4.1 Description of the Study Design

Analytical Observational Study

In analytical observational studies, researchers try to establish an association between

exposure(s) and outcome(s) (10). Depending on the direction of inquiry, these studies can be directed forward, known as cohort studies, or backward known as case-control studies.

The VIOLA Study is an analytical study designed to quantify a relationship or association between two variables – an exposure and an outcome. The exposure, Melody®, is pre-determined for all participants to receive as opposed to experimental studies where an investigator assigns each participant to receive or not receive a particular exposure.

The VIOLA Study was designed to be directed forward using a cohort population at multiple study sites. A cohort is defined as a "group of people with a shared characteristic." In cohort studies, different groups of people with varying levels of exposure are followed over time to evaluate the occurrence of an outcome. Melody® does not have varying levels of exposure but is an overall new exposure for the population.

This observational study will not dictate the cancer screening regimens that the site clinicians and participants utilize. Instead, this study collects data on individuals' cancer screening practices, cancer outcomes, and other factors if needed. Because no regimens are dictated, the VIOLA Study can capture information about and evaluate various cancer screening practices, including the use of different tests or cancer screening regimens.

The association of exposure to outcome this study is attempting to define: How does the use of Melody® before mammography affect participation rates in breast cancer screening?

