5.3 Strategies for Recruitment and Retention

Target sample size:

- An a priori power analysis was conducted using G*Power v3.1.9.2 to determine the minimum sample size required to find significance with a desired level of power set at 0.80 and alpha (α) level at 0.05. Based on this analysis, it was determined that a **minimum of 205 participants** were required to ensure adequate power for a Pearson's Chi-square Test of Independence. (12, 13, 14)

The anticipated site participants' accrual rate will vary; all sites and participants will be located within the United States. Participants will be recruited from outpatient clinics, larger employers, and/or the general public. Participant recruitment venues are site-specific, for example, outpatient clinic monthly clinical breast exam events. Potential participants will be identified and approached using inclusion/exclusion criteria and site-specific events and/or communication channels.

While exact recruitment methods will be specific to each site, the material will be made available in versions suitable for flyers, email, post through social media, or distributed by mail. Forward-facing participant recruitment materials have been submitted separately with indications on how it can be personalization to each site.

The VIOLA Study participants are all women due to the development and validation of Melody®. The objectives and endpoints encourage minorities, employee volunteers, economically disadvantaged, and/or a medically underserved population to participate in the VIOLA Study. The justification for involving vulnerable populations is because they are primarily affected by disparities in the healthcare system. Employee volunteers are included because study sites provide current medical care and have a trusted relationship with the employee volunteer as a current patient.

Careful considerations have been included in the study design and recruitment process to ensure minimal harm/risks and maximum participant protection. Participants will have access to translated study materials and access to additional healthcare navigation if needed. Employers will not be notified of study participation or Melody® results; participation or nonparticipation is confidential. Each participant will receive a \$25 Walmart gift card when completing the VIOLA Study, and there is no cost to participate.

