10.1 Statistical and Analytical Plans

An a priori power analysis was conducted using G*Power v3.1.9.2 to determine the minimum sample size required to find significance with a desired level of power set at 0.80 and alpha (a) level at 0.05. Based on this analysis, it was determined that a minimum of 205 participants were required to ensure adequate power for a Pearson's Chi-square Test of Independence. (12, 13, 14) (Appendix L)

Each participant will be required to take an enrollment survey that collects information on race, ethnicity, and socio-economic status. Participant's addresses will be obtained as part of the requisition process for the CLIA lab, from which information on geographic location can be obtained. In addition to the factors listed above, the enrollment survey also collects information on status and type of health insurance, reproductive health, breast health knowledge, prior screening history, and family and personal history of cancer.

The exit survey has been designed to collect information on the participant experience with Melody® and comprehension of the information Melody® relayed through their site clinician. In addition, information is collected on participant's intention to schedule/participate in future screening mammograms and/or change in intention to participate in a previously scheduled screening mammogram.

Data will be analyzed using SPSS Statistics software. To determine the presence of significant changes, Unpaired T-tests or Mann-Whitney U-test will be used with a significance level set at P < 0.05.

Due to the effect of COVID-19 on screening rates, screening mammogram participation rates will be compared to rates reported for the state of Arkansas in 2019.

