10.4.3 Analysis of the Secondary Endpoints

Analysis of the secondary endpoints will be presented as follows:

Analysis of Secondary Endpoints				
		VIOLA	2019	Total
Site 1	Followed through with screening mammogram	N (% of total for VIOLA)	N (% of total for 2019)	N (% of total)
	Did not follow through with screening mammogram	N (% of total for VIOLA)	N (% of total for 2019)	N (% of total)
P value		P =?		

The analysis will be conducted for each site enrolled in the VIOLA Study.

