Provider: [name], MD
Collecting Location: Namida Lab
Sample ID: MEL21000026
Entered by: [name]

Melody Test

Approved By: [name]

Melody Score **-0.509**

Reference Range:

Melody Score Interpretation **Low**

04/16/21 10:41 AM Melody® is an adjunct clinical test that is intended to be based on the independent medical judgment of the ordering physician in conjunction with the patient's complete medical history and the result of standard care testing. It is recommended that a Melody score above 0.1 be clinically correlated with a structural examination of the breast tissue such as mammography.

Melody is not a replacement for a screening mammogram.

Melody Test type: Composite algorithmic analysis of tear protein biomarkers. Quantitative values of individual biomarkers are not reportable and are not associated with individual biomarker result reference ranges.

Precautions and Limitations:
Melody is intended for women ages 40-87 at average risk of developing breast cancer.

Melody may produce a false positive or false negative result. A Melody score below 0.1 does not guarantee the absence of breast cancer. Patients with a Melody score below 0.1 should be advised to continue participating in breast health standard care testing for their age group. A Melody score above 0.1 does not guarantee the presence of breast cancer. Patients with a Melody score above 0.1 should be referred for imaging.

Melody was developed and its performance characteristics determined by Namida Lab, Inc. It has not been cleared or approved by the U.S. Food and Drug Administration. The FDA has determined that such clearance is not necessary. This test is used for clinical purposes. Namida Lab, Inc. is regulated under the Clinical Laboratory Improvement Amendments of 1988 (CLIA) as qualified to perform high-complexity clinical testing.

J. Study Participant Exit Survey/Questionnaire

**VIOLA Study:
Validating Individualized breast cancer screening
by Offering a new Link in Access**

Study Participant Exit Survey

Thank you for taking the time to participate in our study. Please answer the following questions to the best of your knowledge.

Last Name: _____ First Name: _____ Middle Initial: _____

Date of Birth (mm/dd/yyyy) ____/____/____

1. Before enrolling in the VIOLA Study, did you have an appointment for a screening mammogram?
 Yes No

2. How comfortable were you with the sample collection process? (circle one)

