
G*Power Screen-shots

Screenshots

Moderate Effect Size ($\Delta\% = 20$)

Power = .80

Test family	Statistical test		
z tests	Proportions: Difference between two independent proportions		
Type of power analysis			
A priori: Compute required sample size - given α, power, and effect size			
Input Parameters		Output Parameters	
Tail(s)	Two	Critical z	1.9599640
Proportion p2	.70	Sample size group 1	93
Proportion p1	0.5	Sample size group 2	93
α err prob	0.05	Total sample size	186
Power (1- β err prob)	.80	Actual power	0.8000056
Allocation ratio N2/N1	1		

Power = .85

Test family	Statistical test		
z tests	Proportions: Difference between two independent proportions		
Type of power analysis			
A priori: Compute required sample size - given α, power, and effect size			
Input Parameters		Output Parameters	
Tail(s)	Two	Critical z	1.9599640
Proportion p2	.70	Sample size group 1	107
Proportion p1	0.5	Sample size group 2	107
α err prob	0.05	Total sample size	214
Power (1- β err prob)	.85	Actual power	0.8527234
Allocation ratio N2/N1	1		

Power = .90

Test family	Statistical test		
z tests	Proportions: Difference between two independent proportions		
Type of power analysis			
A priori: Compute required sample size - given α, power, and effect size			
Input Parameters		Output Parameters	
Tail(s)	Two	Critical z	1.9599640
Proportion p2	.70	Sample size group 1	124
Proportion p1	0.5	Sample size group 2	124
α err prob	0.05	Total sample size	248
Power (1- β err prob)	.90	Actual power	0.9000032
Allocation ratio N2/N1	1		

N. Namida Lab, Inc. Policies for PHI Use and Disclosures (HIPAA)

POLICIES AND PROCEDURES FOR PHI USE AND DISCLOSURES

INTRODUCTION

These policies and procedures address handling, safeguarding, using, and disclosing protected health information (PHI). Under HIPAA, covered entities must ensure the privacy of a patients' protected health information.

PHI refers to all information (oral, paper-based documents, and electronic documents) that relates to an individual including but not limited to:

- Medical information
- Billing information
- Financial information
- Names and other identifying information such as:
 - Telephone numbers
 - Fax numbers
 - Electronic Mail addresses

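### Mammograms booked before enrolment are not separated from those booked after Melody; prior appointment is asked only at exit, and no analysis in section 10 uses it

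*Protocol*

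**What the plan says.** Section 4.1 of the protocol puts the study question as "How does the use of Melody® before mammography affect participation rates in breast cancer screening". Section 10.2 tests whether the participation rate exceeds that of 2019. The reference is the Arkansas 2019 rate (10.1) or, for the secondary endpoint, each site's own 2019 rate (10.3).

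Five features bear on this point:

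- **Eligibility.** Nothing in 5.1 or 5.2 excludes a woman who already has a screening mammogram booked.
- **Recruitment.** Section 5.3 names clinics, employers and the general public, and gives "outpatient clinic monthly clinical breast exam events" as an example of a venue.
- **Outcome.** The table in 10.4.3 has two rows per site, "Followed through with screening mammogram" and its negative. Neither refers to when the visit was booked.
- **Prior appointment.** The participant exit survey (Appendix J, item 1) asks "Before enrolling in the VIOLA Study, did you have an appointment for a screening mammogram". The enrolment survey (Appendix D, Section 3) records annual and two-yearly screening habits and the date of the last mammogram, but not a current appointment. Under 10.4.5 the exit survey goes out only after results have been reported to the participant.
- **Use of the answer.** Section 10.1 lists "change in intention to participate in a previously scheduled screening mammogram" among the information collected. No hypothesis, dataset or table in 10.2 to 10.4 uses it.

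**The concern.** For a woman who already holds an appointment, the decision to book came before the exposure. If she attends, her visit can only fall in the followed-through row, alongside visits that the Melody consultation may have prompted. A rise over 2019 can then mean that Melody changed behaviour, or that the women who volunteered were more often already booked. The planned tables cannot tell these apart.

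The timing of the question makes this harder to repair. An answer given after the result may be coloured by it, and women who do not complete the exit survey give no answer. They may also be the women less likely to attend. A later analysis plan could add a stratum, but it could not move the question ahead of the exposure or recover the missing answers.

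**Working it through.** **Reproducing the plan's own figure.** Section 10.1 gives "desired level of power set at 0.80 and alpha (a) level at 0.05". The Appendix L inputs are "Proportion p1 0.5" and "Proportion p2 .70", two-sided, with 1:1 allocation. With pooled variance under the null:

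n per group = [1.960 × √(2 × 0.6 × 0.4) + 0.842 × √(0.5 × 0.5 + 0.7 × 0.3)]² / 0.20² = 93, so 186 in total.

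Adding 10% for drop-out gives 186 × 1.10 = 204.6, rounded up to 205. Both figures reproduce, so the point does not touch the sample-size arithmetic.

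**Model for the booking question.** Let b be the share booked before enrolment, a the attendance among booked women and r the attendance among the rest. Then

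participation rate = b × a + (1 − b) × r.

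The 2019 rate is set at 0.50, the untreated rate in Appendix L. The documents give neither b nor a, so these are assumptions. The central case has 20% booked in 2019 and a = 0.90. Melody has no effect, so r is the same in VIOLA as in 2019:

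r = (0.50 − 0.20 × 0.90) / 0.80 = 0.40.

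| Booked share in VIOLA | Rate in VIOLA | Spurious gain |
|---|---|---|
| 20% (equal to 2019) | 0.18 + 0.32 = 0.50 | 0 |
| 30% | 0.27 + 0.28 = 0.55 | 5 points |
| 40% | 0.36 + 0.24 = 0.60 | 10 points |
| 50% | 0.45 + 0.20 = 0.65 | 15 points |

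The gain equals the excess in booked share × (a − r), here the excess × 0.50.

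**Range.** With 10–30% booked in 2019 and 80–100% attendance among booked women, an excess of 10 points adds 3.3 to 7.1 points, and an excess of 30 points adds 10 to 21 points.

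**Chance of a false claim of an increase (central case, excess of 10 / 20 / 30 points).** A two-sample comparison with 93 per group, as in Appendix L, gives 10% / 28% / 54%. With 205 women set against a fixed rate of 0.50 it is 30% / 82% / 99%. With equal shares it is 2.5% in both cases.

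**Would dropping booked women from VIOLA solve it?** With an equal booked share in both periods and no true effect, the rate among unbooked women is (0.50 − b × a) / (1 − b). For a of 0.80 to 0.90, the contrast with the unrestricted 2019 rate is too low by 3 to 4 points at 10% booked, 8 to 10 points at 20%, and 13 to 17 points at 30%. That exchanges one bias for another.

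**The case against.** The strongest reply is that counting booked women is like for like. The endpoint is total participation, and the 2019 rates also contain mammograms arranged without Melody. This stands: with equal booked shares the inflation is zero.

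Nor do the documents show that booked women are over-represented. Breast exam events are one example of a venue, and the study aims at populations with a record of low mammography attendance, which could point the other way. An excess is plausible when volunteers from clinics and such events are set against a statewide rate, but it is not established.

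It can also be said that the sponsor does collect the variable, that Appendix K item 15 asks providers how many participants scheduled a mammogram after the consultation, and that the analysis may sit in a plan not shown. In part this stands. However, item 15 yields one count per provider, not linked to individual women. Appendix J item 10 asks about scheduling or completing in a single question, so booked and newly prompted women can give the same yes. The timing of item 1 is set by the protocol.

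A reader might infer three stronger things, none of which the documents support:

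- **That the protocol has a rule crediting booked visits to Melody.** No such rule is stated. These visits fall in the row by default because it is silent on booking date.
- **That 50% booked could by itself produce the whole planned 20-point effect.** The sum is 0.5 × 0.9 + 0.5 × 0.5 = 0.70. It needs unbooked women to attend at 50%. With booked women attending at 90%, an overall 2019 rate of 50% would then mean that nobody was booked in 2019. With 20% booked in 2019, the gain at 50% booked is 15 points. Twenty points is reached only at the edge of the assumed range.
- **That Melody can only leave attendance unchanged or lower it in booked women.** The outcome is attendance, and some booked women miss their visit, so Melody could prevent a missed appointment.

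**Conclusion.** The point holds as one of attribution and of when a baseline item is collected. Booked women are eligible, the outcome row does not separate their visits, prior appointment is asked only after the result, and section 10 makes no use of the answer. An observed rise over 2019 therefore cannot be separated from bookings made before exposure.

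An upward bias is conditional, not shown. It arises if the booked share in VIOLA exceeds that in the 2019 reference, and is about 5, 10 or 15 points for an excess of 10, 20 or 30 points. Those sizes rest on an assumed 2019 rate of 50%, 20% booked in 2019, 90% attendance among booked women and no Melody effect. The sample size of 205 is not in question here.

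**What to change.** By amendment:

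1. Move exit item 1 to the enrolment survey (Appendix D, Section 3), so that it is answered before the tear sample.
2. Keep total participation as the quantity compared with 2019.
3. In 10.4.3, prespecify follow-through by appointment at enrolment (yes/no). Report attendance and cancellation in women with an appointment, which also gives the changed-intention item in 10.1 a use. Report new uptake in women without one.
4. Label these results supportive. Do not test the no-appointment group against the unrestricted 2019 rate, given the downward bias of 3 to 17 points shown above.
5. State that an increase over 2019 will not be attributed to Melody without considering the share of women already booked at enrolment.

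The cost is one survey item moved and one stratification added. The supportive subgroups are smaller. As a guide, if only unbooked women were analysed in both groups of the Appendix L calculation, power for 50% against 70% would fall from 0.80 to 0.76, 0.70 or 0.65 at 10%, 20% or 30% booked. That is a further reason to keep these results supportive.

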10.2 Statistical Hypothesis

Primary endpoint:

- H_0 = Participation rates in yearly screening mammography with the incorporation of Melody® (examined by geographic location, socio-economic status, race, and ethnicity) will not be greater than participation rates recorded in 2019.
- H_1 = Participation rates in yearly screening mammography with the incorporation of Melody® (examined by geographic location, socio-economic status, race, and ethnicity) will be greater than participation rates recorded in 2019.

Secondary endpoint:

- H_0 = Participation rates in yearly screening mammography, with the incorporation of Melody® (examined by clinical sites), will not be greater than participation rates recorded

in 2019.

- H_0 = Participation rates in yearly screening mammography, with the incorporation of Melody® (examined by clinical sites), will not greater than participation rates recorded in 2019.

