13.6 Monitoring

The sponsor principal investigator shall select a Monitor(s) qualified by training and experience to monitor the study. A Monitor may be an employee of the principal investigator's organization or an organization contracted by the principal investigator. The Monitor shall assure that the investigators comply with the signed investigator agreement, the Clinical Investigation Plan/Protocol, IDE regulations, and any conditions of approval imposed by the Investigation Site IRB/EC or FDA.

Routine monitoring will occur to:

- Verify that participant enrollment is being achieved.
- Verify that the inclusion/exclusion criteria have been met at enrollment.
- Verify that the participant has signed the correct version of the informed consent.
- Review the medical records of all enrolled participants to ensure all adverse events have been captured and properly reported.

- Verify that the data and imaging are accurate, complete, and backed up by source documents.
- Verify that all contracts, certifications, and medical licenses for each site are valid through the duration of the study.

14. Data Handling and Record-Keeping

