Very Uncomfortable	Uncomfortable	Comfortable	Very Comfortable
1	2	3	4

3. How would you rate the likelihood that you could do the sample collection process on your own? (circle one)

Very Unlikely	Unlikely	Likely	Very Likely
1	2	3	4

4. How would you rate your ability to understand your Melody® results? (circle one)

Very Difficult	Somewhat Difficult	Somewhat Easy	Very Easy
1	2	3	4

5. How would you rate the explanation of your Melody® results by your provider? (circle one)

Unacceptable	Poor	Fair	Excellent
1	2	3	4

6. How would you rate the ability of your provider to answer your questions about Melody®? (circle one)

Unacceptable	Poor	Fair	Excellent
1	2	3	4

7. How would you rate the length of time it took to get your results back from the Melody® test? (circle one)

Unacceptable	Poor	Fair	Excellent
1	2	3	4

8. How would you rate the reliability of the Melody® test? (circle one)

Unacceptable	Poor	Fair	Excellent
1	2	3	4

9. How would you rate your willingness to use Melody® to help you make decisions about your breast health in the future? (circle one)

Very Unlikely	Unlikely	Likely	Very Likely
1	2	3	4

10. After receiving your Melody® results, are you going to schedule/complete a screening mammogram and why?

Yes No

Explanation: _____

11. May we contact you after you participate in the VIOLA Study if you are planning to have a screening mammogram?

Yes No

If yes, please provide the best method of contact (mailing address/phone number /email):

K. Study Site Provider Exit Survey/Questionnaire

**VIOLA Study:
Validating Individualized breast cancer screening
by Offering a new Link in Access**

Study Provider Exit Survey

Site Location ID: _____ Site Location PI: _____

1. How would you rate the process of the sample collection? (circle one)

Very Difficult	Somewhat Difficult	Somewhat Easy	Very Easy
1	2	3	4

2. How would you rate how the understandability of the Instructions for use for collecting tear samples? (circle one)

Very Difficult	Somewhat Difficult	Somewhat Easy	Very Easy
1	2	3	4

3. How would you rate the integration of sample collection in your clinic workflow? (circle one)

Very Difficult	Somewhat Difficult	Somewhat Easy	Very Easy
1	2	3	4

4. How likely do you think an individual could do this collection process at home? (circle one)

Very Unlikely	Unlikely	Likely	Very Likely
1	2	3	4

5. How would you rate the length of time to get results back on Melody®? (circle one)

Unacceptable	Poor	Fair	Excellent
1	2	3	4

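### The primary comparison needs completed mammograms after Melody, but no form or scheduled step shown records completion for each woman, and the follow-up timings conflict

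*Protocol*

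**What the plan says.** **Outcome.** Section 4.2.1 asks whether women given Melody take part in screening mammography at higher rates than in earlier years. The primary hypothesis in section 10.2 concerns "Participation rates in yearly screening mammography with the incorporation of Melody", and section 10.1 says that "screening mammogram participation rates will be compared to rates reported for the state of Arkansas in 2019". The site table in section 10.4.3 has a row for women who "Followed through with screening mammogram" and a row for those who did not. Completion is therefore the intended outcome.

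**Data collection shown.**
- The enrolment survey (Appendix D, breast health, item 5) asks for the date of the last screening mammogram. This is answered before Melody.
- Participant exit survey item 10 (Appendix J) asks "After receiving your Melody® results, are you going to schedule/complete a screening mammogram and why". Section 10.1 describes this survey as collecting "intention to schedule/participate in future screening mammograms".
- Exit item 11 asks permission for later contact, but only if the woman plans a mammogram.
- Provider exit item 15 (Appendix K) asks for one number: how many participants scheduled a mammogram.
- The schedule of events (section 7.3.6) has no row for a mammogram or a record check.

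**Timing.** The Protocol Summary gives six months per participant. The Schematic of Study Design puts enrolment and follow-up both in months 5 to 11 and closure in month 12. Section 10.4.5 sends the exit survey once results have been reported, and section 7.1.4 ends participation when it is completed. Section 10.3 nevertheless speaks of site participation rates seen after the study.

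**The concern.** A woman may complete her exit survey, and so leave the study, before she could have had a mammogram. On the instruments shown, the primary and site tables could then be filled only with stated plans, with an aggregate count of appointments made, or with completions learned from women who had already said they would go. The aggregate count cannot be split by race, ethnicity, income or location, as the primary tables require.

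If completions are collected by some route not shown, the period over which each woman is observed is still not fixed, and no look-back is given for the 2019 rate. A difference from 2019 would then mix any effect of Melody with a difference in what is counted and for how long. An analysis plan can define a derivation, but it cannot supply mammograms that were never recorded or lengthen follow-up after the sites have closed.

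**Working it through.** **1. The plan's own figure.** Appendix L uses 50% v 70%, two-sided 5%, 80% power. With the pooled-variance formula, n per group = [1.960√(2 × 0.6 × 0.4) + 0.842√(0.25 + 0.21)]² / 0.20² = 93, or 186 in total. Then 186 × 1.10 = 204.6, rounded up to 205. Both figures reproduce, so the sample-size arithmetic is not at issue. I borrow 50% and 70% below as illustrative yearly rates, because the 2019 figures are not given.

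**2. What each instrument supplies.**

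| Instrument | After Melody? | Per woman? | Completed? |
|---|---|---|---|
| Enrolment survey, date of last mammogram | No | Yes | Yes |
| Participant exit item 10 | Yes | Yes | No, intention |
| Provider exit item 15 | Yes | No, one total | No, scheduled |
| Exit item 11 | Permission for contact only | Women planning one | Not recorded |
| Schedule of events | No mammogram step | – | – |

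No row meets all three requirements.

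**3. Calendar, if observation stops at closure.** Enrolment runs from the start of month 5 (time 4) to the end of month 11 (time 11).
- Cut at the end of month 11, the last printed follow-up month: follow-up is 0 to 7 months. Six months is possible only for women enrolled by the end of month 5.
- Cut at the end of month 12: follow-up is 1 to 8 months. Six months is possible only for women enrolled by the end of month 6.
- With uniform accrual, the share who can reach six months is 1/7 = 14% or 2/7 = 29%.

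**4. Size of the understatement.** Assumptions: the 2019 figure is a 12-month completion rate, and the cut is at the end of month 12. Let t be a woman's follow-up in months.

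(a) Constant uptake, counting only completions after enrolment: F(t) = 1 − (1 − p)^(t/12), averaged over t uniform on 1 to 8.
- p = 0.70: 9.5% at 1 month, 55.2% at 8 months, mean 35.0%.
- p = 0.50 (no effect): 5.6%, 37.0%, mean 22.4%.
- With the cut at the end of month 11 (0 to 7 months), the means are 28.2% and 17.7%.

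(b) Early uptake, with 80% of the year's completions spread over the first two months and the rest over months 2 to 12. The range runs from uniform accrual over months 5 to 11 to everyone enrolling at the start of month 5.
- p = 0.70: 57.6% to 64.4%.
- p = 0.50: 41.1% to 46.0%.

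(c) Constant uptake, with a 12-month look-back ending at closure that uses the enrolment date of last mammogram. The 50% rate applies before enrolment and 70% after: 1 − 0.30^(t/12) × 0.50^((12 − t)/12), averaged over t uniform on 1 to 8.
- Effect present: 58.6%.
- No effect: 1 − 0.50 = 50.0%, with no understatement.

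The gap between stated intention and completion cannot be computed from the document.

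**The case against.** The strongest defence is that the protocol intends to observe completion. Section 10.3 refers to participation rates seen after the study. Section 4.1 says that the study gathers data on "cancer screening practices, cancer outcomes, and other factors if needed". Section 13.6 has monitors "Verify that the data and imaging are accurate, complete, and backed up by source documents". A case report form is kept for every participant (section 11), and exit item 11 looks beyond the exit survey. A reader might infer from the forms that no completion will be recorded at all. The documents do not support that: the case report form, consent form, study diagram and app screens are not shown, and one of them may hold a field. What remains is that none of the statements cited names a source, a date or a window for a completed mammogram, and item 11 reaches only women who already plan one.

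A reader might also take 1 to 8 months as the study's stated observation period. It is not printed. It is inferred from the calendar, the printed follow-up phase gives 0 to 7, and section 10.3 may mean collection after closure. Nor are both problems certain together: either nothing is recorded after the exit survey, or something is recorded over an unfixed period.

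Finally, a reader might conclude that a real gain would look like a decline, since 35% is below the 50% reference. That holds for constant uptake counted only from enrolment with late accrual. The results script in section 7.3.3 lets the practice offer to schedule a mammogram at once, which favours early uptake, and the enrolment survey already holds the earlier date. In both of those cases a true 70% stays above 50%. If the 2019 look-back is no longer than the observation period, this understatement does not arise.

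**Conclusion.** The point holds, and the protocol should be changed before enrolment. The hypothesis and site table need completed mammograms. After Melody, the instruments shown give intention per woman and a total of women who scheduled, and the only follow-up route is selective. The statements on six-month participation, months 5 to 11 with closure in month 12, participation ending at the exit survey, and rates seen after the study cannot all describe one observation period and must be reconciled.

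The direction of the timing bias is downward if the 2019 figure is a 12-month completion rate and only completions after enrolment count. Its size is uncertain: it depends on the accrual and uptake patterns assumed above and on whether the enrolment date is used. Confidence is moderate, because the absence of a completion field rests on the forms shown.

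**What to change.** 1. Define the primary outcome as a completed screening mammogram for each enrolled woman, whether or not she returns the exit survey. Name the source: site or imaging record, plus contact with all women to find mammograms done elsewhere.
2. Set one fixed window whose look-back matches the definition of the 2019 rate used, and state that definition. One option is a 12-month look-back ending at a fixed time after enrolment, built from the last-mammogram date already collected plus later completions. Say how women screened shortly before enrolment count, since sections 5.1 and 5.2 do not exclude them.
3. Add the step to the schedule of events, and use the same definition for the follow-through rows in section 10.4.3.
4. Remove from exit item 11 the condition that the woman plans a mammogram.
5. Reconcile the Protocol Summary, the Schematic and sections 7.1.4 and 10.3, and set the enrolment stop or the closure so that every woman completes the window.
6. If completion cannot be obtained, report the outcome as stated intention to screen, and drop the test and claim against 2019 participation.

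**Cost.** One data field, a record check or contact per woman, a survey wording change, and an earlier enrolment stop or later closure. The look-back option dilutes the effect, because part of the window precedes Melody. With six months of follow-up and constant uptake, 1 − √(0.30 × 0.50) = 61% against 50%, so a 20-point yearly difference appears as about 11 points. Power should be recomputed for the window and comparator chosen. Relabelling as intention costs only wording and a weaker claim.
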